8.1.5 Adverse event monitoring

The PI will provide the attention and follow-up of the AE presented by the participant until its outcome, according to what is referred to in the following section.

8.1.6 Serious adverse event procedure

The AE care process considers the following stages (Figure 5):

[figure not shown]

Figure 5. Adverse Event Care

During the development and conduct of this study, undesirable harmful events or adverse reactions of medical implication may occur in the research subject, which do not necessarily have a causal relationship with the PIs. These harmful phenomena can occur during the use of investigational drugs at doses authorized for use in humans by a local, national or international regulatory entity. However, it may be suspected that the IP or the investigational drug causes some unwanted clinical manifestation. AEs, ADRs or RAS to one or more medications can occur during the systematic evaluation of the participants (on the days when the clinical review is scheduled, according to the schedule of activities) or suddenly, in such a way that:

1. The investigator must be the first person to whom the patient notifies that he or she has developed or presented any harmful phenomenon of a clinical nature during his or her participation in this study.
2. According to his clinical judgment; Based on the pertinent physical examination, interrogation, etc., as well as the analysis of the information available in the medical literature and what is referred to in the Investigator's Manual, Information to prescribe or Summary of the Comparator Drug Label, the principal investigator determines the pertinent care of the harmful event/reaction.
3. Such care can be in the research center or in the hospital with the greatest resolution power. In such a way that, in the event that the patient is sent by the PI to a hospital, he or she attends through a referral system. The reference can be with a card that identifies the subject as a study participant and links him or her to the pre-established agreement with the institution, or through a medical reference note issued by the PI. Laboratorios Sophia, S.A. de C.V., will pay the expenses for the medical care of the participating patient, when the AE is associated with or is related to the PI or investigational drug.
4. Taking the clinical information collected, either during the care provided at the research center or that provided by the treating physician(s) in the hospital, the PI will record the AE in its clinical note, stating the seriousness, intensity (mild, moderate or severe) and relationship with the product or drug under investigation.
5. The PI must migrate the relevant data to the eCRF and its respective AE section. By virtue of the fact that, in cases of serious AEs, the clinical monitor of the study must be notified within 24 hours

to the knowledge of it, so that in turn it informs the Clinical Team and the UTFLS, and that it subsequently informs the REC. Non-serious AEs will be recorded and appropriately addressed and the safety profile of the IP or investigational drug will be reported to the appropriate regulatory entity in the final report of the clinical trial

The recording of the outcome of the AE depends substantially on the follow-up that the PI performs on the subject, since it is expected that most of the harmful phenomena (consult the investigator's manual) are ophthalmic in nature, however, there may be systemic alterations. Therefore, in the opinion of the researcher, the withdrawal of the participant or their permanence will be considered.

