7.4 Outcome variables

7.4.1 Primary outcome of efficacy

- OSDI test score (ET: day 31).

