7.4.3 Secondary outcome of efficacy

- Changes in the TFRT (ET: day 15 and 31).
- Corneal and conjunctival staining changes with lissamine green (ET:15 and 31).
- Corneal and conjunctival staining changes with fluorescein (ET: days 15 and 31).
- Conjunctival hyperemia changes (ET: day 15 and 31).
- Incidence of chemosis (ET: days 15 and 31).

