7.4.5.2 Tear film rupture time

One of the first aspects of the tear film to change when there is an alteration to the ocular surface is its stability. In general, if the corneal or conjunctival surface is damaged, it is unlikely that a stable tear film can be maintained.

The most common method of assessing tear film stability is fluorescein evaluation of TFRT. Once the fluorescein has been instilled, the cobalt blue filter asks the patient not to blink after blinking 1 to 2 times. The fluorescein-colored precorneal layer will change to less fluorescent or non-fluorescent regions. The time that elapses from the last blink to the appearance of these regions is the TFRT. It will be reported in seconds, in the clinical record and in the eCRF.

Management as AE: a decrease in TFRT of more than 40% compared to baseline should be reported and managed as an AE due to lack of efficacy.

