7.4.6.5 Unscheduled follow-up visits

At the request of the patient or any other individual involved in the study, unscheduled follow-up visits may be conducted for the reporting of AEs. During these visits, all pertinent data on the AEs reported should be collected and, where appropriate, an appropriate management plan should be established.

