8.1.4 Adverse event registration in the electronic case report form

AE registration considers:

- Subject identification information such as: subject number, age, gender, and if applicable

specify the eye.

- Information about the causality of the AE, its relationship to PIs, or to another study-related drug, as appropriate.
- Important date information:
 - Date on which the AE occurs.
 - Date on which the PI becomes aware of it.
 - Date of resolution or outcome, as applicable.
- Information on diagnosis and clinical management.
- If a lack of therapeutic response to PIs is detected, it must be reported as a serious AE within the period stipulated by current regulations. Include in concomitant medications the therapy used for the pharmacological management of the AE.
- Record the outcome or resolution of the event:
 - Recovered/resolved without sequelae
 - Recovered/resolved with sequelae
 - Not Recovered/Unresolved
 - Patient who died due to AEs
 - Patient who died and it is judged that the drug may have contributed
 - Patient who presented death and it is not related to the product or drug under investigation,
 - Unknown
- Information about the investigational product or drug or the drug associated with the AE, AMR, or SRAM. As applicable, the information concerning the generic name, distinctive name or code of the IP and/or investigational drug must be recorded, as appropriate according to the methodological design of the study, this is relevant in the case of blinded studies or in those where placebo is used as comparators, since there are circumstances that justify the opening of the blind to determine if the AE may be attributable to the active agent. the combination of active agents, or the pharmacologically inert substance(s), such as vehicles or additives, as appropriate to the phase of clinical research in which the development of the drug is located. It will also be necessary to include the data concerning the batch number, manufacturing laboratory, expiration date, dose, route of administration, start and end dates of administration and/or consumption, reason for prescription; according to whether it is an investigational product or drug (protocol in which the patient currently participates) or is a drug that the research subject consumes for the treatment of underlying concomitant

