diseases or uses for the management of some transitory sign or symptom that does not correspond to the Natural History of the pathology that motivated his or her entry into the research protocol.

- Indicate the withdrawal or maintenance of the medication, as appropriate. Indicate whether the withdrawal of the IP or investigational drug or suspected drug (of causing the event) eliminates the AE. Also indicate if a dose adjustment is made, if the event changes in terms of intensity or seriousness, persistence of the reaction. It is important to indicate whether in those subjects who are exposed again to the drug, which had previously been discontinued, the AE reappears.
- Information regarding concomitant pharmacotherapy. Indicate the generic name, dose, route of administration, start and end dates of use, as well as the reason for the prescription regardless of whether it is in accordance with the information to prescribe or technical data sheet or is used outside the regulations or what has been authorized by the local, national or international regulatory entity.
- Relevant medical history information. The analysis of the AE considers the information previously narrated, despite the clinical context in which this harmful phenomenon occurs in the participants of the clinical research protocol, is of special interest, so the information about previous conditions, hypersensitivity or allergy phenomena, previous surgical procedures, laboratory analyses or cabinet examinations that have been performed on the participant, etc., that the researcher deems it appropriate to mention may do so.

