10.1.3 Procedure for handling missing data

Safety: The safety assessment will include in the analysis all those subjects (both eyes) who have been exposed at least once to the intervention, regardless of the visit in which they were eliminated from the study (ITT; *Intention To Treat* population).

Efficacy: Those subjects who meet a minimum adherence of 70% will be included in the statistical analysis to meet the objective of the study, taken from the weight of the IP. In cases where the container is not returned, or it has not preserved its physical integrity, adherence will be measured by means of the subject's diary.

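### Participants withdrawn after an adverse event need not give a day-31 OSDI, and adverse events include poor day-15 results on efficacy signs

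*Combined protocol and SAP*

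**What the plan says.** Section 8.1.6 closes with the consequence of an AE: "Therefore, in the opinion of the researcher, the withdrawal of the participant or their permanence will be considered". It gives no criteria. The heading refers to serious events, but the text also deals with non-serious ones. Section 8.1.4 adds: "If a lack of therapeutic response to PIs is detected, it must be reported as a serious AE". Sections 4.1 and 4.2 make the trial open-label, so the investigator knows the dosage.

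AEs and efficacy outcomes overlap. Section 7.4.5.2 says: "a decrease in TFRT of more than 40% compared to baseline should be reported and managed as an AE due to lack of efficacy". TFRT is assessed on days 15 and 31 (7.4.3). Sections 7.4.5.3 to 7.4.5.6 also class as AEs corneal staining of grade III or more, hyperemia of grade 3 or more, and any chemosis. All of these are secondary efficacy outcomes assessed on day 15.

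OSDI is taken at baseline and at the final visit only (schedule in 1.3; 7.4.1; Table 3; 7.4.6.3 and 7.4.6.4). The schedule has no early-exit visit. Unscheduled visits exist for AE reporting: "During these visits, all pertinent data on the AEs reported should be collected" (7.4.6.5).

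The case report form does treat stopping the product as its own item: "Indicate the withdrawal or maintenance of the medication, as appropriate" (8.1.4). In 10.1.3 the safety set holds everyone exposed, "regardless of the visit in which they were eliminated from the study". Efficacy is confined to those with at least 70% adherence (6.4, 10.1.3, 10.1.5). No rule covers a missing efficacy score.

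**The concern.** Stopping the drops and leaving the study are different events. Section 8.1.6 speaks of the participant's withdrawal, and no passage says that someone withdrawn after an AE is still observed to day 31. Several day-15 efficacy findings are AEs by definition and the decision is made unblinded, so whether the primary outcome exists can depend on how the participant was doing and on which dosage they had.

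Two things are at stake. The within-arm criterion in 3.4 (a fall in OSDI of 20% or more in at least one dosage) could be met by those who remain and missed by the arm as randomised. The comparison of dosages could also be distorted if withdrawals differ between arms. An OSDI that was never taken cannot be recovered by analysis.

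**Working it through.** **1. Can a day-15 finding lead to a missing primary outcome?** Set side by side:

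- TFRT is measured on day 15 (1.3, 7.4.3).
- A fall of more than 40% is an AE for lack of efficacy (7.4.5.2), and lack of response is reported as serious (8.1.4), so 8.1.6 applies.
- 8.1.6 permits the participant's withdrawal.
- After withdrawal nothing calls for an OSDI: there is no exit visit in 1.3, and 7.4.6.5 asks for AE data.

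The route is open at every link and compulsory at none. A participant withdrawn at the day-15 visit still has day-15 TFRT, staining and hyperemia. What is lost is the day-31 OSDI, together with day-31 signs, BCVA, IOP and AE assessment.

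**2. How large could the effect be?** The plan gives no withdrawal rate, so there is no figure of its own to reproduce. The nearest is the loss allowance in 10.2.2: 39 × 1.2 = 46.8, rounded to 47, which leaves 47 − 39 = 8 per group. Section 10.1.4 describes those losses as loss to follow-up or withdrawal of consent. Withdrawal by the investigator is not named.

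Let w be the share of an arm withdrawn, c the mean percentage change in completers and d the change the withdrawn would have shown. Then

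whole-arm mean = (1 − w) × c + w × d.

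Take c = −20%, the planned effect. Assume d between 0% (no change) and +40% (the OSDI rise beyond which 7.4.5.1 declares lack of effectiveness). Assume w of 5%, 10% or 20%, and similar baseline OSDI in completers and withdrawn.

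| w | w × 47 | d = 0% | d = +40% |
|---|---|---|---|
| 5% | 2.35 | 0.95 × (−20) = −19% | −19 + 2 = −17% |
| 10% | 4.7 | 0.90 × (−20) = −18% | −18 + 4 = −14% |
| 20% | 9.4 | 0.80 × (−20) = −16% | −16 + 8 = −8% |

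The last row exceeds the allowance of 8 of 47 (17%) for all losses. If the withdrawn would have improved as completers did (d = −20%), the difference is zero.

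**3. Would collecting the score be enough?** If adherence is counted against the full 30 days, a participant fully adherent until stopping at day 15 reaches 30/60, 60/120 or 90/180 applications, which is 50% in every arm. Across the visit window the range is 14/30 = 47% to 16/30 = 53%. The threshold needs 0.70 × 30 = 21 days. Such a participant leaves the efficacy set even with a day-31 OSDI. Only those who stop after about day 21 would stay in. If adherence is instead prorated to the exit date, the participant could qualify but, once withdrawn, would have no post-baseline OSDI to analyse.

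**The case against.** The other side has good points, and several stand.

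- **Withdrawal is optional.** Section 8.1.6 names staying in as an equal possibility, and no passage directs withdrawal for a fall in TFRT. A reader might infer that day-15 failures never reach the day-31 OSDI. The text does not support that: anyone retained does.
- **A day-15 failure is on a sign.** OSDI worsening can be seen only at the final visit. Section 6.1.2.1 itself cites a study in which signs did not differ but symptoms did. A participant with poor TFRT need not have a poor OSDI, so the gap is an assumption.
- **Some follow-up is already required.** AEs are followed to their outcome (8.1.3, 8.1.5), and no passage excuses a participant who is off drops but still enrolled from the final visit. This covers the retained participant. For the withdrawn one it shows that contact continues, but it does not ask for OSDI.
- **Neighbouring wording should not be over-read.** The phrase in 10.1.3 on leaving the study defines the safety set and is not a removal rule. The AE data in 7.4.6.5 may well include the sign concerned.
- **Tolerability withdrawals may be few.** Expected AEs are mild and brief (7.4.5.7).
- **Collection alone would not alter the efficacy result** for most early stoppers, given the 70% rule. This stands and shapes the fix.

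Figure 5, the AE-care diagram in 8.1.6, is not shown in the text available. If it provides for an exit OSDI, the gap is smaller.

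**Conclusion.** The concern holds in this form: an unblinded investigator may withdraw a participant after an AE, AEs include poor day-15 results on efficacy signs, and the text requires neither an exit OSDI nor follow-up to day 31 after withdrawal. Missing primary outcomes can therefore depend on efficacy signs and tolerability.

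The size is not known. With 10% of an arm withdrawn and assumed changes of 0% to +40%, a completer mean of −20% stands for −18% to −14% in the whole arm, which would miss the 20% criterion. This rests on the assumed share, the assumed change in the withdrawn and similar baselines.

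A reader might infer a bias of up to half the effect sought: a 15-point excess in withdrawal percentage times a 15-point OSDI gap is 2.25 points, against 20% of a mid-range baseline of 22.5, which is 4.5. The documents do not support that. Both inputs are assumed extremes, and the ratio sets a between-arm bias against a within-arm change. The gap would also put the withdrawn at 18 + 15 = 33, which is 47% above baseline and beyond the plan's own 40% threshold for lack of effectiveness.

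This is a worthwhile, inexpensive improvement. It does not show that the primary result will be wrong.

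**What to change.** In 8.1.6 and 10.1.3, separate stopping the product from leaving the study. Leave the decision to stop drops as it is.

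- Participants who stop drops stay for the remaining scheduled visits, including day-31 OSDI, signs, BCVA, IOP and AEs.
- Those who will not continue are offered the final-visit assessments, OSDI included, at last contact, with date and reason recorded.
- Add a supportive OSDI analysis of all randomised participants by assigned dosage using these data, and state beforehand how scores still missing are handled. Without it, the 70% rule keeps most early stoppers out of any efficacy result.
- List those who stopped or left by dosage and reason, with their OSDI.

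The cost is protocol wording, case report form fields for the date and reason, and one further analysis and listing. The day-31 visit and its assessments are already scheduled. The day-31 data on AEs, BCVA and IOP also complete the all-exposed safety set. The downside is small: some day-31 scores will be off treatment and must be flagged. The questionnaire asks about the past week (Annex 16.1), so a participant who stops near day 15 gives a wholly off-treatment score.

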8.1.7 Causality evaluation

Causality assessment is the methodology used to estimate the probability of attributing the observed AE to a drug. It considers probabilistic categories according to the available evidence and the quality of the information, based on national pharmacovigilance regulations. [54]

The Pharmacovigilance and Technovigilance Unit of Laboratorios Sophia, S.A. de C.V. (UFTLS) can use the Karch and Lasagna algorithm modified by Naranjo referred to by Aramendi I, as a tool to facilitate the probabilistic categorization of causality. In this algorithm, different items are qualified, which allow assigning a value to the cause-effect relationship between the administration of the drug and the adverse reaction. [57] See Table 4. Karch and Lasagna's algorithm modified by Naranjo.

No.	Reagent	Score	
		Yes	No
1.	There are conclusive prior reports of adverse drug reaction, adverse event, or suspected adverse drug reaction	+1	0
2.	The adverse event appeared when the suspected drug was administered	+2	-1
3.	Adverse drug reaction, adverse event, or suspected adverse drug reaction improved by stopping or administering a specific antagonist	+1	0
4.	Adverse drug reaction/adverse event/suspected adverse drug reaction reappeared upon administration of the investigational drug/product/investigational drug	+2	-1
5.	There are alternative causes that can cause this reaction	-1	+2
6.	Adverse reaction/adverse event/suspected adverse drug reaction occurred after placebo administration	-1	+1
7.	The drug was determined in blood or other fluids at toxic concentrations	+1	0
8.	The intensity of adverse reaction/adverse event/suspected adverse drug reaction was higher at higher doses or lower at lower doses	+1	0
9.	The patient has had similar reactions to the investigational drug/product or investigational drug in the past	+1	0
10.	Adverse reaction/adverse event/suspected adverse drug reaction confirmed with some objective evidence	+1	0
Total score			Sum
Probabilistic category based on the score obtained			
I	The causal relationship is verified	≥9	
II	The AMR is likely due to the investigational drug or product	5 to 8	
III	AMR may be due to the investigational drug or product	1 to 4	
IV	The causal relationship is doubtful	0	

Each item receives a defined score and the final sum allows estimating the probabilistic category of the cause-effect relationship between the administration of the investigational product and the adverse reaction, adverse event or suspected reaction Adverse.

Table 4. Karch and Lasagna's algorithm modified by Naranjo

In such a way, the degree of certainty to establish the IP as the causal agent of the harmful phenomenon that occurs to the subject of the clinical study. It can also be indicated directly

by the PI based on their clinical experience or through the voluntary application of the tool mentioned above. However, it is important for the researcher and the UFTLS to consider the following arguments in favor of causation:

- a) Strength of association, which refers to the number of cases in relation to those exposed.
- b) The consistency of the data, i.e., the presence of a common characteristic or pattern.
- c) The exposure-effect pattern, which determines the relationship with the site of appearance, time, dose and reversibility after deletion.
- d) Biological plausibility, which refers to the possible pharmacological or pathophysiological mechanisms involved in the development or presentation of the AE.
- e) Experimental findings, e.g., the appearance of abnormal metabolites or high levels of the drug or its biotransformation product.
- f) Analogy, which refers to the experience gained with other related drugs, adverse reactions frequently produced by the same family of pharmacological agents.
- g) Nature and characteristics of the data, i.e., objectivity, accuracy and validity of the relevant documentation. [58]

8.1.8 Unanticipated problems

Unanticipated problems (UAPs) consider those situations that pose risks to the participating subjects, in general, any incident, experience or result that meets all the following criteria:

- Unexpected in terms of its nature, severity, or frequency in relation to: 1) study-related documents such as the investigator's manual, study protocol, and informed consent form; and 2) the characteristics of the population being studied.
- Related or possibly related to your participation in the study (possibly related means that there is a reasonable possibility that the incident, or results, was caused by study procedures).
- Indicative that the research places participants at a higher risk of harm (including physical, psychological, economic, or social) than previously recognized.

8.1.8.1 UAPs Report

The PI will be responsible for reporting UAPs to the sponsor, RC, REC. The report must contain the following information:

- Identification of the study: protocol title and number, name of the IP and, if applicable, of the center.
- Detailed description of the event, incident, experience, or outcome.
- Explanation, justification of the reasons why the incident represents an UAP
- Description of changes to the protocol or corrective actions taken or proposed in response to the UAP.

UAPs that are serious AEs must be reported to the IEC and the sponsor within the first 24 hours of the PI becoming aware of it.

Any other UAPs will be reported to the IEC and the sponsor within the first 5 business days after the PI becomes aware of it.

9. Study monitoring

The study sponsor is responsible for monitoring the study. Monitoring activities include, but are not limited to: general safety monitoring, general study quality monitoring, monitoring by study site, detection monitoring, reporting and tracking of AEs, monitoring for resolution of discrepancies in data capture, etc.

Responsibility for monitoring activities and ultimate responsibility for monitoring rests with the sponsor.

The details of the monitoring activities are specified in a separate document from this protocol in a Monitoring Plan.

